6.3. Lifestyle Restrictions

6.3.1. Meals and Dietary Restrictions

- Refrain from consumption of red wine, Seville oranges, grapefruit or grapefruit juice, and/or pomelos, exotic citrus fruits, grapefruit hybrids, or fruit juices from 7 days before the start of study treatment until after collection of the final PK or PD sample.

6.3.2. Caffeine, Alcohol, and Tobacco

- During each dosing session, participants will abstain from ingesting caffeine- or xanthine-containing products (eg, coffee, tea, cola drinks, and chocolate) for at least 24 hours before the start of dosing until after collection of the final pharmacokinetic (PK) and/or pharmacodynamic sample.
- During each dosing session, participants will abstain from alcohol for 72 hours before the start of dosing until after collection of the final PK and/or pharmacodynamic sample. Participants will also abstain from alcohol 72 hours before the 14 ± 2 days follow up procedures have been completed, and 72 hours before the 32 ± 2 days follow-up procedure as well as the 62 ± 2 days LFT follow up procedures have been completed.
- Use of tobacco products will not be allowed from screening until after the final follow-up visit.

6.3.3. Activity

- Participants will abstain from strenuous exercise for 48 hours before each blood collection for clinical laboratory tests. Participants may participate in light recreational activities during studies (eg, watching television, reading).

6.3.4. Exposure to UV

Initial photochemical data suggest that a potential photoreactive risk may exist. As a precaution, until this risk is further assessed via experimental evaluation, patients receiving GSK3335065 should avoid being in strong direct sunlight and/or UV exposure or use protective clothing, sunscreen and sun glasses from dosing till the follow-up visit.

6.4. Screen Failures

Screen failures are defined as participants who consent to participate in the clinical study but are not subsequently randomized in the study. A minimal set of screen failure information is required to ensure transparent reporting of screen failure participants to meet the Consolidated Standards of Reporting Trials (CONSORT) publishing requirements and to respond to queries from regulatory authorities. Minimal information includes demography, screen failure details, eligibility criteria, and any serious adverse events (SAEs).

Individuals who do not meet the criteria for participation in this study (screen failure) are allowed to be rescreened once after consultation with the Sponsor.

7. TREATMENTS

Study treatment is defined as any investigational treatment(s), marketed product(s), placebo, or medical device(s) intended to be administered to a study participant according to the study protocol.

7.1. Treatments Administered

Study Treatment Name:	GSK3335065	Placebo
Dosage formulation:	GSK3335065 Solution for injection	Placebo to match GSK3335065 Solution for injection
Unit dose strength(s)/Dosage level(s):	Unit dose strength : 5 mg/mL stock that may be diluted Dosage levels : variable	N/A
Route of Administration	Intravenous injection and infusion	Intravenous injection and infusion
Dosing instructions:	Study medication may be diluted in 0.9% w/v Sodium Chloride and will be administered by intravenous infusion by study personnel following specified regimens	Study medication will be administered by intravenous infusion by study personnel following specified regimens
Packaging and Labeling	Study Treatment will be provided in a carton containing 1x GSK3335065 5mg/ml, 5mL vial. Each carton will be labeled as required per country requirement.	Study Treatment will be provided in a carton containing 1x Placebo to match GSK3335065, 5mL Vial. Each carton and vial will be labeled as required per country requirement.
Manufacturer	GlaxoSmithKline Manufacturing SpA, Parma	GlaxoSmithKline Manufacturing SpA, Parma

7.2. Dose Modification

In case a dose reduction is necessary, the study treatment will be administered as follows:

- This protocol allows some alteration from the currently outlined dosing schedule, but the maximum predicted exposures will not exceed the 75-fold exposure margin in terms of AUC to the rat NOAEL as defined in the 14-day preclinical GLP tox studies.
- The decision to proceed to the next dose level of GSK3335065, will be made by the GSK Study Team based on safety, tolerability and available pharmacokinetic and/or pharmacodynamic data obtained in at least 6 subjects on GSK3335065 at the prior dose level. The actual doses to be administered may be adjusted based on safety, tolerability and preliminary pharmacokinetic and/or pharmacodynamic data at previous dose levels; these dose adjustments may involve either an increase or a decrease in the planned dose.
- The dosing schedule may also be adjusted to expand a dosing cohort to further evaluate safety, tolerability, pharmacokinetic and/or pharmacodynamic findings at a given dose level, or to add cohorts to evaluate additional dose levels. The study procedures for these additional subject(s) or cohort(s) will be the same as that described for other study subjects.
- If the same Serious Adverse Event (SAE) occurs in more than one subject, the dose escalation will be temporarily halted and no further subject will be dosed until a full safety review of the data has taken place. Relevant reporting and discussion with the Medical Monitor, relevant GSK personnel, and with the Ethics Committee will then take place prior to any resumption of dosing.
- The above criteria will apply even if measured pharmacokinetic parameters are below the above mentioned PK stopping criteria, and every effort will be made to take a blood sample at the time of the event for pharmacokinetic analysis in the presence of any of the above events.

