1. SYNOPSIS

Protocol Title: Randomized, Double-blind, Placebo-controlled Dose Escalation Study to Evaluate Safety, Tolerability, Pharmacokinetics, and Pharmacodynamics of Single Doses (intravenous bolus) and constant intravenous infusion over 7 Days of GSK3335065 in Healthy Adult Subjects

Short Title: Safety, Tolerability, Pharmacokinetics, and Pharmacodynamics investigation of GSK3335065 (IV) in healthy adults

Rationale: GSK3335065 is being developed as a treatment for acute pancreatitis with the intent of reducing 3-hydroxykynurenine (3HK) levels to the normal range (or lower) and maintaining them at this level throughout the 7-day treatment period.

Objectives and Endpoints:

Objective	Endpoint
Primary	
 To determine the safety and tolerability of GSK3335065 administered as a single IV bolus (Part A and C), and as a constant IV infusion over 7 days (Part B and C) in healthy volunteers
Secondary	
 Adverse event / Serious Adverse event monitoring Laboratory parameters (hematology, clinical chemistry, urinalysis) 12-lead ECG parameters (PR, QRS, QT, QTcF, etc.) Vital signs (systolic and diastolic blood pressure, heart rate) 
 To determine the pharmacokinetic characteristics of GSK3335065 administered as a single IV bolus (Part A and C), and as a constant IV infusion over 7 days (Part B and C) in healthy volunteers Determine dose/exposure effects of GSK3335065 on KMO inhibition (pharmacodynamics) in healthy volunteers (All Parts) 
 Pharmacokinetic Parameters: $AUC_{(0-t)}$, $AUC_{(0-\infty)}$, t_{last}, C_{max}, C_{avg}, t_{max}, CL, V, $t_{1/2}$ Evaluate changes in levels of TRP metabolites (3HK and KYN)

Overall Design: This is a phase I, first time in human (FTIH), three part, randomized, placebo-controlled dose escalation study that will utilize an adaptive design for combining Single Ascending Dose (SAD) by IV bolus (Part A) with Ascending Doses by intravenous (IV) continuous infusion dosing for 7 days (Part B) in healthy males. Part C will recruit women of non-child bearing potential (WONCBP) only, and a single dose by

IV bolus will be investigated prior to multiple dose (7 day) being investigated. The decision to proceed to the next dose level in Part A will be based on safety and tolerability data obtained up to 8 days post dose from at least 6 subjects at the prior dose level.

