Liver changes	
In rats, there was centrilobular hepatocyte hypertrophy and increased liver weight at ≥ 140 mg/kg/day; and additional liver pathology changes and increases in aspartate aminotransferase, alanine aminotransferase activity and total bilirubin concentrations at ≥ 300 mg/kg/day.
 
GSK3335065 is a carboxylic acid and has the potential to form reactive acyl glucuronide metabolites which could contribute to idiosyncratic liver toxicity. An in vitro assay in human liver microsomes showed there was no turnover of GSK3335065 in microsomes and no acyl glucuronides were detected. However, an
	
Subjects with ALT or bilirubin $>1.5 \times$ULN prior to dosing will be excluded (isolated bilirubin $>1.5 \times$ULN is acceptable if bilirubin is fractionated and direct bilirubin $<35\%$). (Exclusion Criterion #1).
 
Subjects with current or chronic history of liver disease, or known hepatic or biliary abnormalities (with the exception of Gilbert's syndrome or asymptomatic gallstones) will be excluded (Exclusion Criterion #2).
 
Monitoring for ALT, AST, alkaline phosphatase and bilirubin at each dose level (Section 2 Time

Potential Risk of Clinical Significance	Summary of Data/Rationale for Risk	Mitigation Strategy
	
acyl glucuronide with a measured half-life of 2 hrs was detected in rat plasma following 7 days continuous infusion. Therefore there is a risk that this metabolite may be formed in humans. This might be of clinical concern if the total daily dose exceeds 100 mg.
	
and Events Table)
 
Stopping criteria based on LFT increases (Section 8).
 
The NOAEL for these effects is 75-fold the highest exposures proposed in this study.
 
The highest dose proposed in this study is 73.4 mg total dose on day 1 followed by 50.4 mg total dose/day (Above signals are considered an increased concern if daily dose is ≥ 100 mg).
 
Selected plasma PK samples generated during Part A will be subjected to additional analysis in order to determine if any acyl glucuronides are present. In addition, plasma, urine and bile samples will be used to generate full metabolic profiles in samples taken during the study.

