5.1.1. Part A: Single Ascending Dose (IV Bolus) in males

Part A is a randomized, double-blind (Sponsor unblinded), placebo-controlled, single intravenous ascending dose study to evaluate the safety, tolerability, pharmacokinetics and pharmacodynamics of GSK3335065 in healthy male subjects. Part A was initiated using an interlocking crossover design. 8 Healthy male subjects (6 active, 2 Placebo) were assigned to one of two cohorts (Cohorts 1 and 2). Subjects in cohorts 1 received a single dose of 0.1 mg GSK3335065, and subjects in cohort 2 received a single dose of

0.25 mg GSK3335065. All subjects from cohorts 1 and 2 will be discontinued from the study.

To facilitate subject recruitment, the design of Part A will be changed to a parallel cohort design and dosing will be continued at the third dose level (1.3 mg). For each cohort of 8 subjects at each dose, 6 subjects will receive active drug and 2 subjects will receive placebo using a predefined allocation schedule. Hence, each subject in cohorts 3-8 will receive one active dose strengths or placebo in a parallel study design according to the dose escalation scheme described in a latter section.

Characterization of the GSK3335065 PK relationship will be performed based on emerging data from lower dose levels to ensure that anticipated exposures will not exceed an approximately 75-fold exposure margin in terms of AUC to the rat NOAEL.

Characterization of the PD response to GSK3335065 may be performed on an ongoing basis or reviewed at the completion of Part A.

Sentinel dosing: In Part A, the first 2 subjects in each cohort will act as sentinels. One of these subjects will be randomized to active treatment, and the other will receive placebo. At least 24 hours will elapse (relative to the start of dosing) before administration of GSK3335065 to the subsequent subjects at the same dose level to allow for assessment of potential adverse experiences. This assessment will include evaluation of safety parameters including physical examination findings, 12-lead Electrocardiogram (ECGs), clinical laboratory tests and clinical monitoring for adverse events. If there are no clinically relevant safety or tolerability concerns, the remaining 6 subjects in the same dosing session will receive the dose.

Table 4 Study Duration of Cohorts 1 and 2 (Part A)

Screening	All screening assessments to be completed within 28 days prior to the first dose.

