6.1. Inclusion Criteria

Participants are eligible to be included in the study only if all of the following criteria apply:

Age

1. Participant must be 18 to 50 years of age inclusive, at the time of signing the informed consent. In Part C (WONCBP) participants must be between 18 and 60 years of age.

Type of Participant and Disease Characteristics

2. Participants who are overtly healthy as determined by medical evaluation including medical history, physical examination, laboratory tests, and cardiac monitoring.
3. A subject with a clinical abnormality or laboratory parameter(s) which is/are not specifically listed in the inclusion or exclusion criteria, outside the reference range for the population being studied may be included only if the investigator in consultation with the Medical Monitor if required agree and document that the finding is unlikely to introduce additional risk factors and will not interfere with the study procedures.

Weight

4. Body weight >50kg and body mass index (BMI) within the range 18.5 – 32 kg/m² (inclusive).

Sex

5. Abstinence/contraceptives: Length of time required for abstinence or use of contraceptives should take into account the reproductive toxicity profile including genotoxicity and teratogenicity, the size of the molecule, and the number of doses.

a. Male participants:

A male participant must agree to use contraception as detailed in [Appendix 5](#) of this protocol during the treatment period and for at least 2 days after the last dose of study treatment and refrain from donating sperm during this period.

b. Female participants:

Only female participants of non childbearing potential (WONCBP) as defined in [Appendix 5](#): Contraceptive Guidance and Collection of Pregnancy Information are eligible to participate.

Informed Consent

6. Capable of giving signed informed consent as described in [Appendix 3](#) which includes compliance with the requirements and restrictions listed in the informed consent form (ICF) and in this protocol.

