6.2. Exclusion Criteria

Participants are excluded from the study if any of the following criteria apply:

Medical Conditions

1. Alanine transaminase (ALT) and bilirubin >1.5xULN (isolated bilirubin >1.5xULN is acceptable if bilirubin is fractionated and direct bilirubin <35%).
2. Current or chronic history of liver disease, or known hepatic or biliary abnormalities (with the exception of Gilbert's syndrome or asymptomatic gallstones)

3. QTcF >450 msec from a mean of triplicate readings taken no more than 2 minutes apart
4. Clinically significant abnormal echocardiogram
5. The participant has a history or current evidence of depression, bipolar disorder, suicidal ideation and behaviour, or a lifetime history of suicide attempt.
6. cTn or BNP >ULN

Prior/Concomitant Therapy

7. Use of prohibited medication (Section 7.7 & Section 7.8)

Prior/Concurrent Clinical Study Experience

8. The subject has participated in a clinical trial and has received an investigational product within the following time period prior to the first dosing day in the current study: 30 days, 5 half-lives or twice the duration of the biological effect of the investigational product (whichever is longer).
9. Exposure to more than four new chemical entities within 12 months prior to the first dosing day

Diagnostic assessments

10. Presence of hepatitis B surface antigen (HBsAg), positive hepatitis C antibody test result at screening or within 3 months prior to first dose of study treatment. For potent immunosuppressive agents, subjects with presence of hepatitis B core antibody (HBcAb) should also be excluded.
11. A positive pre-study drug/alcohol screen.
12. A positive test for human immunodeficiency virus (HIV) antibody.
13. Where participation in the study would result in donation of blood or blood products in excess of 500 mL within 84 days.

Other Exclusions

14. Poor or unsuitable venous access
15. History of regular alcohol consumption within 6 months of the study defined as:
An average weekly intake of >14 units. One unit is equivalent to 8 g of alcohol: a half-pint (~240 mL) of beer, 1 glass (125 mL) of wine or 1 (25 mL) measure of spirits.
16. History of sensitivity to any of the study medications, or components thereof or a history of drug or other allergy that, in the opinion of the investigator or Medical Monitor, contraindicates their participation.
17. History of smoking within 6 months of the study.

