11. APPENDICES

11.1. Appendix 1: Protocol Deviation Management and Definitions for Per Protocol Population

Inclusion Criteria

Number	Inclusion Description
1	Participant must be 18 to 50 years of age inclusive, at the time of signing the informed consent. In Part C (WONCBP) participants must be between 18 and 60 years of age.
2	Participants who are overtly healthy as determined by medical evaluation including medical history, physical examination, laboratory tests, and cardiac monitoring.
3	A subject with a clinical abnormality or laboratory parameter(s) which is/are not specifically listed in the inclusion or exclusion criteria, outside the reference range for the population being studied may be included only if the investigator in consultation with the Medical Monitor if required agree and document that the finding is unlikely to introduce additional risk factors and will not interfere with the study procedures.
4	Body weight >50kg and body mass index (BMI) within the range 18.5 – 32 kg/m ² (inclusive).
5	Abstinence/contraceptives: Length of time required for abstinence or use of contraceptives should take into account the reproductive toxicity profile including genotoxicity and teratogenicity, the size of the molecule, and the number of doses. Male participants: A male participant must agree to use contraception as detailed in Appendix 5 of the protocol during the treatment period and for at least 2 days after the last dose of study treatment and refrain from donating sperm during this period. Female participants: Only female participants of non childbearing potential (WONCBP) as defined in the protocol Appendix 5: Contraceptive Guidance and Collection of Pregnancy Information are eligible to participate.
6	Capable of giving signed informed consent as described in Appendix 3 which includes compliance with the requirements and restrictions listed in the informed consent form (ICF) and in this protocol.

Exclusion Criteria

Number	Inclusion Description
1	Alanine transaminase (ALT) and bilirubin >1.5xULN (isolated bilirubin >1.5xULN is acceptable if bilirubin is fractionated and direct bilirubin <35%).
2	Current or chronic history of liver disease, or known hepatic or biliary abnormalities (with the exception of Gilbert's syndrome or asymptomatic gallstones)
3	QTcF >450 msec from a mean of triplicate readings taken no more than 2 minutes apart
4	Clinically significant abnormal echocardiogram

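### Two safety thresholds are inconsistently worded: exclusion criterion 1 joins ALT and bilirubin with *and* where *or* is meant, and five statements of the six-subject escalation minimum omit that the six must be on active drug

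*Protocol*

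**What the plan says.** **Liver entry.** Exclusion criterion 1 in Protocol 6.2 reads "Alanine transaminase (ALT) and bilirubin >1.5xULN (isolated bilirubin >1.5xULN is acceptable if bilirubin is fractionated and direct bilirubin <35" (the last figure is a percentage). SAP 11.1 copies it: "Alanine transaminase (ALT) and bilirubin >1.5xULN". The liver row of the risk table in Protocol 3.3.1 cites Exclusion Criterion #1 by number but opens with "Subjects with ALT or bilirubin". Two inclusion criteria in 6.1 bear on the same subject. Criterion 2 admits "Participants who are overtly healthy as determined by medical evaluation including medical history, physical examination, laboratory tests, and cardiac monitoring". Criterion 3 gives the investigator discretion over "A subject with a clinical abnormality or laboratory parameter(s) which is/are not specifically listed in the inclusion or exclusion criteria".

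**Escalation minimum.** Protocol 7.2 bases the decision on "data obtained in at least 6 subjects on GSK3335065 at the prior dose level" and gives that decision to the GSK Study Team. Five other places state the minimum as "from at least 6 subjects at the prior dose level", with no arm named: the synopsis, 5.4.1 (Part A), 5.4.2 (Part B), and the Part A and Part B escalation paragraphs of Appendix 3. Appendix 3 gives the decision to a Dose Escalation Committee that includes the Principal Investigator. Section 5.1 sends the reader to Appendix 3 for escalation. On cohort make-up, 5.1.1 says that "6 subjects will receive active drug and 2 subjects will receive placebo using a predefined allocation schedule".

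**The concern.** These are an entry threshold and an escalation threshold in a first-in-human study of a compound with liver findings in rats.

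On entry, the literal criterion excludes only subjects in whom both analytes are raised. Section 6 bars eligibility waivers, so the criteria have to be applied as written. SAP 4.1 reports eligibility deviations from the inclusion/exclusion page, so a subject with an isolated high ALT who was assessed literally would not appear there as a deviation.

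On escalation, one decision carries two different minimums and two different owners. A reader who works from Appendix 3 or 5.4 would apply the weaker minimum. The stricter text is also hard to find, because the list in 7.2 is introduced as dealing with dose reduction. Placebo subjects say nothing about tolerability of the dose, so what matters for escalation is the number on active.

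**Working it through.** **1. Criterion 1, texts side by side**

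| Place | Connective | Isolated ALT above 1.5xULN |
|---|---|---|
| Protocol 6.2 | and | not excluded, read literally |
| SAP 11.1 | and | not excluded, read literally |
| Protocol 3.3.1 | or | excluded |

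The criterion carries an exception for isolated raised bilirubin. Under *and*, raised bilirubin alone would never exclude, so the exception would have nothing to do. It is needed only under *or*. The intent is therefore *or*, and the two operative copies are wrong.

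Inclusion criterion 2 is a judgement of overt health, not a numerical limit. Inclusion criterion 3 covers parameters not listed among the criteria. ALT is listed, so that route arguably does not apply. Neither supplies the 1.5xULN limit.

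**2. Cohort arithmetic**

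Plan's own total (5.2, 10.2.1): 8 cohorts x 8 + 4 x 8 + 2 x 8 = 64 + 32 + 16 = 112, as stated. Each cohort has 6 active and 2 placebo.

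**3. What each wording requires**

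- Section 7.2: six on active, which in a standard cohort means every active subject.
- The other five statements, read alone: any six of eight. The fewest on active is 6 − 2 = 4.

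Number of six-subject sets from 6 active and 2 placebo: C(8,6) = 28.

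- 4 active: C(6,4) x C(2,2) = 15
- 5 active: C(6,5) x C(2,1) = 12
- 6 active: C(6,6) = 1

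If both sentinels (1 active, 1 placebo) are in the set, the other four come from 5 active and 1 placebo: C(6,4) = 15 sets, of which 10 have 4 active in all, 5 have 5, and none has 6. These are counts of possible sets, not probabilities. If all eight subjects have data, all six active subjects are included and the two wordings agree.

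**4. Worst-case illustration**

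With no event among n active subjects, the one-sided 95% upper bound on the event rate is 1 − 0.05^(1/n).

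| n on active | Upper bound |
|---|---|
| 6 | 1 − 0.05^(1/6) = 0.393 |
| 5 | 1 − 0.05^(1/5) = 0.451 |
| 4 | 1 − 0.05^(1/4) = 0.527 |

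The difference between 6 and 4 is 0.527 − 0.393 = 0.134. It arises only if 7.2 is disregarded and two active subjects lack data while both placebo subjects have it.

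**5. Replacement, if fewer than six active subjects have data**

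- Protocol 5.2: replacement allowed with sponsor approval; no exception for Part A.
- Protocol 10.2.1: names replacement only for Part B and Part C Cohort 8. That label is stale: Cohort 8 is now the 54 mg cohort of Part A, and the Part C infusion cohort is 14.
- SAP 11.7.1: excludes replacement in Part A Cohorts 3-8.
- Protocol 7.2: separately allows a cohort to be expanded.

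**The case against.** The strongest reply is that no protection is missing. Section 7.2 applies alongside the other texts, so meeting every text means meeting the stricter minimum, and the cost is then zero. Appendix 3 keeps the sponsor's committee members unblinded, so they can see how many subjects were on active. For criterion 1, the risk table and the criterion's own exception make the meaning plain, and the requirement of overt health on laboratory tests gives a second check. On this view these are editorial slips.

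Most of that stands, and it limits the practical effect. It does not make the texts right. No passage says whether 7.2 or Appendix 3 prevails, and 5.1 points to the looser one. Treating 7.2 as the intended minimum is itself an inference, though six active per cohort supports it. For ALT, the reader has to correct the operative criterion from a background table.

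A reader might infer that withdrawn subjects in Part A Cohorts 3-8 could not be replaced, leaving expansion as the only remedy. The documents do not support that. Section 5.2 permits replacement generally, 10.2.1 does not forbid it in Part A, and the SAP was written after the study had been terminated, so it could not govern conduct. The texts conflict and need aligning.

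**Conclusion.** Both wordings are wrong in current operative text and worth correcting, with limited practical effect.

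- **Criterion 1.** Read literally, it omits the intended limit on isolated ALT. No numerical effect is claimed; the documents give no screening ALT data.
- **Escalation minimum.** There are two minimums and two named decision-makers for one decision. Read alone, the five looser statements could be met with 4 on active.

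A reader might take the gap between 39% and 53%, about 13 percentage points, as information that the plan gives up at each escalation. It is not. It describes a worst case that would breach 7.2. The bounds assume independent subjects and no observed events, and the documents give no rate of missing data from which to say how likely the case is.

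A reader might also infer that the study escalated on too few active subjects or enrolled subjects with raised ALT. Nothing in the documents shows either. The SAP introduction records that the study was terminated after sentinel dosing of Part A Cohort 3, so few escalation decisions were ever taken.

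**What to change.** 1. In Protocol 6.2, criterion 1, change *and* to *or* between ALT and bilirubin, and make the same change in SAP 11.1.
2. Add the qualifier that the six subjects are on GSK3335065 in the synopsis, 5.4.1, 5.4.2 and both Appendix 3 escalation paragraphs.
3. In 7.2, name the Dose Escalation Committee as decision-maker, to match Appendix 3.
4. State what happens when fewer than six active subjects have data: expand the cohort under 7.2, or replace under 5.2 with sponsor approval. Bring 10.2.1 and SAP 11.7.1 into line with 5.2, and correct the Part C label in 10.2.1 from Cohort 8 to Cohort 14.

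These are text edits. No analysis changes, and the planned 112 is unaffected unless a cohort is expanded or subjects are replaced. The cost is a possible delay to a cohort, or a few extra subjects in it, when fewer than six on active have data.
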